3.2 Rationale for study design, doses and control groups

This is a Phase I study to investigate the metabolism, excretion, and PK of $[^{14}C]$ AZD8931 in man and the number of subjects is based on the desire to gain adequate information whilst exposing as few subjects as possible to the investigational product and procedures. Therefore, 6 subjects will be enrolled for this study.

Healthy subjects are considered appropriate for this study because the data obtained will not be influenced by any disease process or concomitant medication which would inevitably be present in patients. Entry will be restricted to subjects who have not been exposed to significant amounts of radiation as part of their occupation or from other sources such as X-rays.

The design of this study is standard for this type of study.

The age range (\geq 50 years) is higher than normally used in studies in healthy subjects, which is in accordance with the Administration of Radioactive Substances Advisory Committee (ARSAC) policy for studies where radioactive material is given. The age range is chosen to minimise the risk of disruption to fertility possibly caused by the radiation.

Healthy subjects will receive one oral dose of a solution of [¹⁴C] AZD8931 (nominal total dose of no more than 160 mg AZD8931, 200 μ Ci/7.4 MBq). A dose of 160 mg AZD8931 was selected to give an adequate concentration of radioactivity for quantification of AZD8931 routes of excretion and metabolism. In the AZD8931 clinical programme, exposure to AZD8931 has increased proportionally with doses from 40 to 160 mg AZD8931 in healthy subjects and patients. A single dose of 160 mg AZD8931 was also investigated in the food effect study (Study D0102C00011). Therefore, a dose of 160 mg will provide information regarding excretion and metabolism that can be extrapolated to lower dose levels. The dose vessel will be rinsed with 2 x 50 mL water which must also be taken by the subject. This will give an effective dose equivalent of 4.7 mSv which falls within the radiolabeled category II dose, World Health Organisation (WHO) 1977 and category IIb, International Commission on Radiological Protection (ICRP) 1992 guidelines.

Although 40 mg twice daily has been chosen as a clinically feasible dose for long-term dosing, AZD8931 has been well tolerated as single oral doses ranging from 2.5 mg up to 200 mg in healthy male subjects.

Sampling times for PK assessments and the duration of the sampling period for blood, urine, and faeces are based on the clinical data from previous studies with AZD8931 and radioactivity studies in pre-clinical species. The duration of the collection has been chosen to ensure that virtually no radioactivity remains to be excreted after the sampling is completed.

4. SUBJECT SELECTION CRITERIA

The Investigator should keep a record, the subject screening log, of subjects who entered pre-study screening.

Each subject should meet all of the inclusion criteria and none of the exclusion criteria for this study. Under no circumstances can there be exceptions to this rule.

4.1 Inclusion criteria

For inclusion in the study subjects should fulfil the following criteria:

- 1. Provision of signed, written, and dated informed consent before any study specific procedures
- 2. Healthy male subjects aged 50 to 65 years, inclusive
- 3. Subjects should be non-smokers or ex-smokers who have stopped smoking for >3 months before Visit 1 and have not used nicotine products for >3 months
- 4. Regular daily bowel movements (ie, production of at least one stool per day)
- 5. Body mass index (BMI) between 19 and 30 kg/m², inclusive
- 6. Weight between 50 and 100 kg, inclusive
- 7. Suitable veins for cannulation or repeated venepuncture

4.2 Exclusion criteria

Subjects should not enter the study if any of the following exclusion criteria are fulfilled:

- 1. Previous allocation to treatment in the present study
- 2. History of any clinically significant disease or disorder which, in the opinion of the Investigator, may either put the subject at risk because of participation in the study, or influence the results or the healthy subject's ability to participate in the study
- 3. History or presence of gastrointestinal, hepatic, renal disease, surgical procedure, or any other condition known to interfere with the ADME of drugs
- 4. Any clinically significant illness, medical/surgical procedure or trauma within 4 weeks before dosing
- 5. Any clinically significant abnormalities in physical examination, vital signs, or clinical laboratory assessments as judged by the Investigator

- 6. Positive results on screening tests for serum hepatitis B surface antigen, hepatitis C antibody, or human immunodeficiency virus (HIV)
- 7. Inadequate bone marrow reserve as demonstrated by an absolute neutrophil count $\leq 2.5 \times 10^9/L$ and platelet count $\leq 200 \times 10^9/L$
- 8. Any clinically important abnormalities in rhythm, conduction, or morphology of a resting ECG with a measureable QTc interval of >450 msec twice within a 24-hour period, as judged by the Investigator
- 9. Known or suspected history of significant drug abuse
- 10. Positive screen for drugs of abuse at screening (excluding alcohol) or on admission (including alcohol) to the study centre
- 11. History of alcohol abuse or excessive intake of alcohol defined as regular weekly intake of 28 units of alcohol or more (1 unit=25 mL spirits, 125 mL wine, 250 mL beer or lager)
- 12. History of severe allergy/hypersensitivity or ongoing allergy/hypersensitivity, as judged by the Investigator, or history of hypersensitivity to AZD8931, its excipients, or drugs with a similar chemical structure or class
- 13. Use of any prescribed or non-prescribed medication including drugs with hepatic enzyme-altering properties, such as St John's wort, antacids, analgesics, herbal remedies, vitamins, and minerals during 2 weeks (or longer depending on the medication's half-life) before dosing until after Follow-up. Occasional use of paracetamol and non-steroidal nasal decongestant is permitted at the discretion of the Investigator.
- 14. Blood donation within 1 month before screening or any blood donation/blood loss greater than 500 mL during the 3 months before screening
- 15. Receipt of another new chemical entity (defined as a compound which has not been approved for marketing) or participation in any other clinical study that included drug treatment within 3 months before dosing in this study, or participation within 1 month of dosing in this study in a methodological study where no drugs were administered. Note: The period of exclusion begins at the time of the post-study medical examination of the previous study. Subjects consented and screened but not dosed in a previous Phase I study are not excluded based on this criterion.
- 16. Judgement by the Investigator that the subject should not participate in the study if the subject is considered unlikely to comply with study procedures, restrictions, or requirements

- 17. Subjects who are unwilling to use one of the recommended highly effective methods of contraception during the study and for 3 months after dosing
- 18. Subjects who are exposed to radioactivity as part of their occupation
- Subjects who have been exposed to radiation levels above background (eg, through X-ray examination) of >5 mSv in the last year, >10 mSv in the last 5 years, or a cumulative total of >1 mSv per year of life
- 20. Participation in a previous radiolabelled study within the 12 months before screening
- 21. Involvement in the planning or conduct of the study (applies to both AstraZeneca, , and study centre staff)
- 22. Prior diagnosis of dry eye syndrome, or an eyelid or eyelash abnormality
- 23. Subjects who have used contact lenses within 6 weeks before screening and who require the use of contact lenses during the study
- 24. History or current evidence of any of the following:
 - Any eye injury in the previous 3 months or a prior eye injury still associated with persistent or recurrent symptoms or impairment of vision
 - Corneal surgery (laser refractive surgery performed more than 3 months before the start of the study is allowed and should be recorded in the surgical history)
 - Orbital irradiation
 - Collagen vascular, chronic inflammatory, or degenerative disease with eye involvement (eg, rheumatoid, Sjögren's syndrome, systemic lupus erythematosus)
 - Clinically significant ocular surface disease, ie, diseases of the conjunctiva and cornea (including atopic keratoconjunctivitis, Stevens-Johnson syndrome, ocular cicatricial pemphigoid, or chemical burns, Herpes simplex, or Herpes zoster virus eye disease)
- 25. Evidence of maculopathy in subjects with impaired visual acuity defined as best corrected near visual acuity <0.4 and/or best corrected distance visual acuity (including pinhole) <0.7, in one or both eyes
- 26. Current diagnosis of acneform, psoriasis, or severe atopic eczema rash requiring treatment

Genetic research exclusion criteria:

- 1. Previous allogenic bone marrow transplant
- 2. Non-leukocyte depleted whole blood transfusion within 120 days of genetic sample collection.

Procedures for withdrawal of incorrectly enrolled subjects see Section 5.3.

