AZD8931 was not genotoxic in either in vitro or in vivo assays.

On repeat administration of AZD8931 in rats, gastrointestinal toxicity was dose limiting. Epithelial degeneration and atrophy, consistent with the pharmacology of the compound, was evident on histopathological examination of a number of tissues including the skin and gastrointestinal and genitourinary tracts. There was evidence of reversibility following a 4-week recovery period.

In dogs, repeat administration of AZD8931 was associated with epithelial degeneration and atrophy in the cornea, skin, gastrointestinal tract, and genitourinary tract. These findings are consistent with the pharmacology of AZD8931 and there was evidence of reversibility of findings following a 4-week recovery period.

Dose limiting toxicity on repeat administration in the dog was corneal epithelial ulceration and in the 1-month study resulted in the termination of one high dose animal following 7 days of dosing due to a severe ulceration. In surviving animals recovery of less severe corneal ulceration was observed in life, despite continued dosing. In a single ascending dose (SAD) study in the dog, corneal translucency was observed in life but a mild corneal epithelial ulceration was seen on histopathology. Gastrointestinal toxicity was dose limiting in the SAD study.

In vitro assays indicate a potential for QT-prolongation and arrhythmia with AZD8931. There was no evidence of QT-prolongation in the in vivo cardiovascular studies. Intravenous administration of AZD8931 in an anaesthetised dog model at a dose of 30 mg/kg resulted in hyperkalaemia with associated electrocardiogram (ECG) waveform changes. Hyperkalaemia was not seen following oral dosing to conscious dogs. Reductions in arterial blood pressure were also observed at this dose level in anaesthetised dogs. In a dog SAD study, at doses of 7.1 mg/kg and above, AZD8931 produced reversible reductions in arterial blood pressure.

Dose related increases in plasma glucose, generally accompanied by increases in plasma cortisol have been observed in dogs following oral administration of AZD8931. Hyperglycaemia had reversed by 24 hours. The insulin response to hyperglycaemia appeared to be attenuated at high plasma levels of AZD8931.

A potential photo toxicity risk with AZD8931 has been identified based on the light absorption profile of the compound and a positive result in the fibroblast 3T3 cell assay.

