6.2 Data collection and enrolment

Each subject will undergo screening in the 28 days before Visit 2. This will consist of:

- 1. Obtaining written informed consent before starting any study specific procedures
- 2. Recording of demographic data (date of birth, sex, race)
- 3. Height, weight, and calculation of BMI
- 4. A standard medical, medication, and surgical history with review of the inclusion and exclusion criteria with the subject
- 5. A complete physical examination
- 6. Habits of nicotine and alcohol use
- 7. Vital signs
- 8. Recording of a resting 12-lead paper ECG
- 9. A blood sample for routine clinical chemistry and haematology, and screen for hepatitis B surface antigen, antibodies to hepatitis C virus and antibodies for HIV
- 10. A urine sample for routine urinalysis and drugs of abuse screen (excluding alcohol)
- 11. Assessment of AEs
- 12. Assessment of any concomitant medication
- 13. Ophthalmology assessment
- 14. Blood sample for pharmacogenetics (optional)

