For ECG parameters, the QT correction factor will be based on the Fridericia's formula. Further categorical summaries of absolute QT and QTcF values (more than 450 ms, more than

480 ms, and more than 500 ms) and change from predose values in QT and QTcF values (more than 30 ms, and more than 60 ms) will also be produced.

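### Exclusion 8 joins its ECG-abnormality condition and its QTc condition by the word 'with', so as written it excludes only subjects who have both

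*Protocol*

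**What the plan says.** Exclusion 8 (Section 4.2) is one sentence with two elements. The first is "Any clinically important abnormalities in rhythm, conduction, or morphology of a resting ECG". The second follows directly: "with a measureable QTc interval of >450 msec twice within a 24-hour period", with the judgement left to the investigator. The criterion does not say which QT correction applies.

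Two other exclusions come near this ground. Exclusion 5 covers "Any clinically significant abnormalities in physical examination, vital signs, or clinical laboratory assessments as judged by the Investigator", a list that leaves out the ECG. Exclusion 2 covers "History of any clinically significant disease or disorder which, in the opinion of the Investigator, may either put the subject at risk", which depends on history and opinion and mentions neither ECG nor QTc.

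Sections 4 and 5.3 both say that the selection criteria admit no exceptions.

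At screening, Section 6.2 lists one item: "Recording of a resting 12-lead paper ECG". Table 1 marks the next ECG at Day 1 predose and none on Day -1. Section 12.2.2 states for the analysis that "the QT correction factor will be based on the Fridericia's formula".

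Section 1.1 gives the reason for attention to the QT interval: "In vitro assays indicate a potential for QT-prolongation and arrhythmia with AZD8931". It adds that the in vivo cardiovascular studies showed no such effect.

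**The concern.** An entry criterion that allows no exceptions has to be readable in only one way. Here the connecting word makes the two elements cumulative, whereas a reader would expect an ECG exclusion to act on either finding. A site that applies the text as written could enrol a man whose QTc has been confirmed above the protocol's own limit, or one with an important conduction abnormality and a QTc within it. A site that reads the sentence the other way would exclude both. The protocol does not settle which is meant.

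What is at stake is subject selection for a compound with a stated in vitro QT and arrhythmia signal, and whether it can be shown afterwards that the criterion was applied correctly. The absorption, metabolism and excretion results do not depend on it.

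**Working it through.** The plan states no figure on this point, so there is nothing to reproduce. The check is a logical one on the wording, followed by two comparisons between sections.

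**1. The wording.** Let A be a clinically important abnormality of rhythm, conduction or morphology, and B a QTc above 450 msec twice in 24 hours (both from exclusion 8).

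| A | B | As written (A and B) | As separate limbs (A or B) |
|---|---|---|---|
| yes | yes | excluded | excluded |
| yes | no | not excluded | excluded |
| no | yes | not excluded | excluded |
| no | no | not excluded | not excluded |

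Three rows contain an abnormal finding. The text as written excludes 1 of the 3, and separate limbs would exclude 3 of the 3. The two readings differ in the second and third rows.

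**2. Other criteria that might catch those rows.** Exclusion 5 lists three kinds of assessment, and the ECG is not among them. Exclusion 2 could catch a subject only if the investigator regards the finding as a significant disease or disorder. Section 6.3.7.1 sends ECG abnormalities, among which it counts QTc values, for qualified review, but attaches no consequence for eligibility.

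**3. The QTc term.** Exclusion 8 names no correction. The only correction in the protocol is Fridericia, in Section 12.2.2, where it is stated for the analysis. The missing piece is a link between the two sections.

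**4. The repeat reading.** Two ECGs are scheduled before dosing: screening (Section 6.2, Table 1) and Day 1 predose (Table 1, footnote h). Screening may be up to 28 days before Day 1. The two lie within 24 hours of each other only if screening is done within 24 hours of the predose ECG. In the ordinary case the second reading must come from an unscheduled repeat, and no section says when that repeat is taken.

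**The case against.** The strongest reply is that the intention is plain. The connecting word may have been meant as 'including', Section 6.3.7.1 treats QTc values as a type of ECG abnormality, and the criterion leaves room for the investigator's judgement. Subjects must also be healthy, and exclusion 2 gives a general safeguard. This has some weight: in practice an investigator may well exclude such a subject. It does not repair the text. If a prolonged QTc counts as an abnormality in itself, the third row of the table closes but the second stays open. Only reading the connecting word as 'including' or 'or' closes both, and the sentence does not say that. Exclusion 2 is an indirect safeguard.

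Three stronger readings are tempting, and the documents do not support them.

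- A reader might infer that the twice-in-24-hours condition can never be met. A confirmatory ECG would be triggered by a first high value, so it need not appear in Table 1, and Section 12.2.2 anticipates unscheduled and repeat measurements.
- A reader might infer that entry uses a different QT correction from the analysis. No other formula appears anywhere in the protocol.
- A reader might infer that the post-dose QTcF summary would be blurred by subjects who enter above 450 msec. The ECG baseline is Day 1 predose (Section 11.1), which even a perfectly worded screening criterion would not control. Section 12.2.2 also tabulates changes from predose of more than 30 and more than 60 ms.

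The risk should not be overstated either. Section 1.4 reports no QTc change of clinical concern in the single-dose study up to 200 mg, and no clinically relevant ECG change in the food-effect study, which used 160 mg.

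**Conclusion.** The point holds as a fault of wording in a stated safety criterion. As written, exclusion 8 acts only on the combination of both findings. It leaves out an isolated confirmed QTc above 450 msec and an important ECG abnormality with a QTc of 450 msec or less, and no other criterion names the ECG.

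The conclusion rests on reading the connecting word literally, which the no-exceptions rule makes the natural reading for a site. Its size is one of three abnormal combinations excluded. How many of the six subjects could be affected cannot be estimated from the protocol. The missing reference to a correction formula and the unstated timing of the repeat ECG are secondary gaps to be reconciled; neither is an error on its own. The primary objective is not affected. The criterion should be corrected because the change is cheap, but the background findings do not make it urgent.

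**What to change.** Reword exclusion 8 as two separate limbs, one for abnormalities of rhythm, conduction or morphology and one for the QTc interval, and state whether each excludes on its own. In the same change, reconcile the QTc term with the correction given in Section 12.2.2, and reconcile the twice-in-24-hours condition with the single screening ECG in Table 1 and Section 6.2 by saying when the second reading is taken. The threshold and the clinical rule are for the sponsor to decide, and none is proposed here.

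The cost is a change of protocol wording, with an occasional repeat ECG or an extra screen failure as the possible downside.

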5. STUDY CONDUCT

5.1 **Restrictions during the study**

Subjects will be required to:

- Subjects must be willing to use barrier methods of contraception (condom or occlusive cap with spermicidal foam/gel/film/bream/suppository), unless their partners are post-menopausal, surgically sterile, or are using acceptable contraceptive methods (oral contraceptive, implant, long-term injectable contraceptive, or intra-uterine device). In addition, subjects must agree to continue to take similar contraceptive precautions until 3 months after the dose of AZD8931
- Abstain from donating sperm for 3 months after dosing
- Abstain from donating blood during the study and for at least 3 months after the last visit
- Abstain from using drugs of abuse
- Use sunglasses (where possible) and skin cream with an ultraviolet light wavelength A (UVA) and ultraviolet light wavelength B (UVB) protection with a sun factor of >30 if exposed to sunlight and avoid the use of sun tanning booths during the study and for 3 months after dosing
- Caffeine-containing drinks or foods (eg, coffee, tea, cocoa, chocolate, and cola) are permitted during the study but the level of intake should not be changed
- Abstain from eating sweet corn, tomato skin, and chewing gum
- Abstain from drinking alcohol from 72 hours before admission to the study centre continuing until discharge from the study centre and also from 72 hours before the follow-up assessments
- Abstain from consuming poppy seeds from enrolment until after the follow-up assessments

- Fast from 2 hours before the planned start of dosing until 2 hours after dosing. Water is allowed up to 1 hour predose and from 1 hour after dosing (except for water used to rinse the dosing vessel). Subjects should also be fasted from 2 hours before safety blood and safety urine sample collection throughout the study
- Remain in the study centre for 10 days after dosing and should return to the study centre for the follow-up visit
- Refrain from strenuous activity that is not within their normal weekly routine beginning from 72 hours before screening and 5 days before admission to the study centre until after the follow-up assessments have been performed
- Refrain from actively trying to lose weight from screening until after Follow-up
- While resident in the study centre subjects will receive a high fibre diet

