events were reported for 21 of the 24 healthy subjects (88%) participating in the study. Skin-type AEs were reported by 75% of the subjects. Skin-type AEs, excluding application site reactions, were reported by 67% of the subjects. All of the skin-type AEs were considered to be mild (Common Terminology Criteria for Adverse Events [CTCAE] grade 1), except for the macular rash (CTCAE grade 2) reported by the subject who was discontinued from the study. There were no clinically relevant changes in potassium, glucose, other safety laboratory variables, vital signs, ECG, or physical examination.

For this current study subjects will be instructed to use sunscreen (with a sun factor of >30) for up to 3 months after administration of the investigational product due to the phototoxicity risk. Baseline and postdose ophthalmology assessments, and ad hoc AE-triggered assessments will be performed to monitor ocular surface and vision effects.

Further information regarding the benefit/risk profile can be found in the Investigator's Brochure.

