6.3.5 Laboratory safety assessment

Blood and urine samples for determination of clinical chemistry, haematology, and urinalysis will be taken at the times indicated in Table 1.

The laboratory variables that will be measured are listed in Table 2.

Clinical chemistry	Haematology	Urinalysis
Serum (S)-Albumin	Blood (B)-Haemoglobin	Urine (U)-Haemoglobin
S-Alanine aminotransferase	B-Haematocrit	U-Protein
S-Aspartate aminotransferase	B-Erythrocyte	U-Glucose
S-Alkaline phosphatase	B-Leukocyte	U-Creatinine
S-Bilirubin, total	B-Leukocyte differential count	
S-Calcium, total	(absolute)	
S-Cholesterol	B-Platelet count	
S-Creatinine	B-Red cell count	
S-C-reactive protein	B-Reticulocyte count	
S-Glucose, fasting	B-Mean corpuscular volume	
S-Potassium	B-Mean corpuscular haemoglobin	
S-Sodium	B-Mean corpuscular haemoglobin	
S-Gamma glutamyltransferase	concentration	
S-Urea		
S-Free thyroxine		
S-Thyroid stimulating hormone		

Table 2Laboratory safety variables

The samples for clinical chemistry, haematology, and urinalysis will be analysed using routine methods at

Blood will be tested for hepatitis B surface antigen, antibodies to hepatitis C virus, and antibodies to HIV at the screening visit.

Urine will be tested at the screening visit and Day -1 for the following drugs of abuse: alcohol (only Day -1), methadone, cannabis, cocaine, benzodiazepines, amphetamine, methamphetamines (including ecstasy), opiates, barbiturates, phencyclidine, and tricyclic antidepressants. The test will be performed at the study centre. If a subject tests positive for drugs of abuse a retest will be performed, and they may be excluded from entering the study, as judged by the Investigator.

If any laboratory values outside the

reference limits are suspected to be of clinical significance, as judged by the Principal Investigator and/or AstraZeneca, the sampling will be repeated. Subjects in whom the suspected clinical significance is confirmed at repeated sampling will either not be included or, if already included (started treatment), the deviating values will be monitored until normalisation or for as long as the Investigator considers necessary.

For blood volume see Section 7.1

6.3.6 **Physical examination**

Physical examinations will be performed at the times indicated in Table 1.

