11. EVALUATION AND CALCULATION OF VARIABLES

11.1 Calculation or derivation of safety variable(s)

All AEs will be collected for each subject from the time when informed consent is obtained (Visit 1) until the follow-up visit. Adverse events that occur before dosing will be reported separately.

Change-from-baseline variables will be calculated for the safety variables listed below, as the post-treatment value minus the value at baseline. The baseline values will be as follows:

• Clinical laboratory tests: Day -1

- Vital signs (including supine and standing blood pressure): Day 1 predose
- ECG: Day 1 predose

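### Table 2 calls the glucose test fasting, but Section 5.1 requires only a 2-hour fast, so baseline and postdose glucose could differ in meal state

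*Protocol*

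**What the plan says.** Table 2 (Section 6.3.5) gives the glucose test as "S-Glucose, fasting". No other analyte in the table carries a fasting qualifier.

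Section 5.1 sets the fast for safety samples: "Subjects should also be fasted from 2 hours before safety blood and safety urine sample collection throughout the study". Its separate rule for dosing is of the same length: "Fast from 2 hours before the planned start of dosing until 2 hours after dosing".

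Table 1 places safety laboratory tests at screening, Day -1 (the day of admission), 24 hours postdose, Day 11 and follow-up. Section 11.1 fixes the baseline: "Clinical laboratory tests: Day -1". Section 12.2.2 plans summaries of absolute values and changes from baseline where applicable, listings with out-of-range values flagged, and shift tables for laboratory values.

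Section 1.1 explains why glucose is of interest: "Dose related increases in plasma glucose, generally accompanied by increases in plasma cortisol have been observed in dogs following oral administration of AZD8931". It adds that the insulin response appeared attenuated at high plasma levels, and that "Hyperglycaemia had reversed by 24 hours".

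**The concern.** The label promises a fasting result, but the sampling rule guarantees only 2 hours without food. Time since the last meal then has a lower limit and no upper one, and nothing keeps it similar across visits. A subject could have eaten shortly before the 2-hour limit on the admission day and had no food overnight before the 24-hour sample, or the reverse, and comply on both occasions.

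A baseline taken after a meal could mask a rise in glucose. A baseline taken after a long fast, followed by a post-meal sample, could produce an apparent one. The design has no control group to separate the two. Meal state is also settled when the blood is drawn, so a later analysis plan cannot restore it.

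The laboratory outputs matter here because Section 6.3.3 makes a deterioration in a mandated laboratory value an adverse event only if it meets a seriousness criterion or leads to discontinuation. A non-serious glucose change would appear mainly in the laboratory summaries and listings.

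**Working it through.** The plan states no figure on this point, so the check is mainly a comparison of the text.

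1. **Which fast governs glucose?** Section 5.1 has two fasting rules, one around dosing and one before safety samples. Both are 2 hours. Sections 6.3.5 and 6.2 and the Table 1 footnotes add no longer fast, so the 2-hour rule is the only one that applies to the glucose sample.

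2. **Does fasting in Table 2 simply mean that rule?** The 2-hour rule covers every safety blood and urine sample. If the qualifier meant only that, it would apply to every analyte and add nothing to glucose. The more natural reading is that a stricter condition was intended and never written down.

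3. **Is meal state the same at baseline and later?**

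| Sample | Setting | Time since last meal | Clock time |
|---|---|---|---|
| Screening | before admission | at least 2 h | not set |
| Day -1 (baseline) | day of admission | at least 2 h | not set |
| 24 h postdose | resident | at least 2 h | follows the dosing time |
| Day 11 | resident, day of discharge | at least 2 h | not set |
| Follow-up | after discharge | at least 2 h | not set |

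The lower limit is the same in every row and there is no upper limit. Comparability between rows is therefore possible but not assured.

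4. **Could it be corrected afterwards?** Section 10 says that, for laboratory data, the electronic CRF holds only the date and time of sampling. No section asks for the time of the last meal.

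5. **How large could the effect be?** This rests on an assumption, because the documents give no glucose values, standard deviation or meal times. Let a meal 2 to 3 hours earlier raise glucose by *d* mmol/L over the fasted value, with *d* between 0 and 2. Let *k* of the 6 subjects differ in meal state between baseline and a later sample, all in the same direction. The shift in mean change is *k* × *d* / 6:
   - *d* = 0: shift 0 for any *k*
   - *d* = 1, *k* = 3: 3 × 1 / 6 = 0.5 mmol/L
   - *d* = 2, *k* = 3: 3 × 2 / 6 = 1.0 mmol/L
   - *d* = 2, *k* = 6: 6 × 2 / 6 = 2.0 mmol/L

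   The sign depends on which sample is the post-meal one. If the differences run in both directions, they partly cancel in the mean and appear as extra spread. Nothing in the protocol shows which *d* or *k* would occur.

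6. **Would a stricter fast let the trial see the dog signal?** Section 1.1 has that signal reversed by 24 hours, and the first postdose laboratory sample is at 24 hours. An acute rise of that kind could be over before the first sample under any fasting rule.

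**The case against.** The strongest reply is that the protocol uses the word fast for 2 hours throughout and never defines fasting glucose as overnight. On that view the label is loose but not contradictory, and calling 2 hours too short imports a laboratory convention. This stands in part: no sentence of the protocol says that 2 hours is insufficient for glucose. It does not explain why glucose alone carries the qualifier, and it does not make meal state comparable between visits.

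The second reply is that the risk is small on the protocol's own evidence. The glucose finding comes from dogs and had reversed by 24 hours. For the food-effect study in 24 healthy subjects at the same 160 mg dose, Section 1.4 reports: "There were no clinically relevant changes in potassium, glucose, other safety laboratory variables, vital signs, ECG, or physical examination". Section 1.4 also reports no clinically relevant clinical chemistry changes in the 40 healthy men given single doses up to 200 mg. Section 6.3.5 has values suspected of clinical significance repeated, so a striking outlier would be checked. All of this stands and limits the weight of the point.

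Three stronger readings are tempting, and the documents do not support them:

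- A reader might infer that the samples would be post-meal and that the glucose change would be driven by meals. Two hours is a minimum, so the text permits this and does not bring it about.
- A reader might infer that the fasting rule is what stops the trial from speaking to glucose. The 24-hour sampling time limits detection of an acute rise in any case.
- A reader might infer that out-of-range flags would be wrong whichever way the samples fall. The visible text does not say that the reference limits are fasting limits, and a sample that really was fasted would be flagged correctly against such limits.

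**Conclusion.** The point holds as a minor one. Table 2 and Section 5.1 do not agree on the condition under which glucose is measured, and the rule as written allows the Day -1 baseline and later samples to differ in meal state. Glucose change from baseline and the shift tables could then be confounded by meal timing in 6 uncontrolled subjects.

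The effect is confined to one variable, summarised descriptively, under the secondary safety objective. No hypothesis is tested, and the primary mass balance and pharmacokinetic objective is unaffected. The size is unknown. The 0 to 2 mmol/L range above is an assumption that includes zero, and the upper end also needs all six subjects to differ in the same direction. The conclusion itself rests only on the absence of any further fasting rule, meal schedule or last-meal record in the protocol.

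**What to change.** Reconcile Section 5.1 with Table 2 in one of two ways.

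- Define one fasting condition for the glucose sample. Apply it at a similar clock time to the existing Day -1, 24-hour, Day 11 and follow-up samples, and to screening.
- Or keep the 2-hour rule, remove the fasting label from Table 2, record the time of the last meal with each sample, and interpret glucose changes and flags as non-fasting.

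The baseline should not be moved to a new Day 1 predose sample. Table 3 counts 5 chemistry samples, matching screening, Day -1, 24 hours, Day 11 and follow-up. A Day 1 predose sample would therefore be a sixth (5 mL, taking the planned total from 217.5 to 222.5 mL) or would displace the Day -1 one. A longer fast at that point could also alter the fasting condition at dosing, which bears on the primary objective.

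The cost is protocol wording, plus one recorded item under the second option, with no added sample or visit. The practical downside of the first option is that samples may have to be taken before a meal on the admission day and at follow-up.
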